## 3.3 Primary, secondary, and additional study outcomes

3.3.1 **The first primary outcome of the study (PA1) is the presence or absence of chronic LBP.** This is determined through the patients' answers to a two-item Chronic LBP Questionnaire based on criteria developed by the NIH Task Force on research standards for chronic LBP. The questions are: 1) How long has low back pain interfered with your ability to do regular daily activities? 2) Think only about the past 6 months. How often has low back pain interfered with your ability to do regular daily activities? Chronic LBP is defined as a response of "more than three months" to question 1, and a response of "half the days or more than half the days" in the past 6 months to question 2.

3.3.2 **The second primary outcome of the study (PA2) is the Oswestry Disability Index.** Originally described by Fairbanks et al, the Oswestry LBP Questionnaire is a reliable, well-validated, easily-administered, disease-specific measure that results in an index of a patient's perceived level of function due to LBP and is based on ten areas of performance. Items include how the back pain impacts the patient's ability to care for themselves (washing, dressing, etc.), lift, walk, sit, stand, and sleep. It also assesses the effect of the pain on the patient's sex life (if applicable), social life, and ability to travel. Patient

stakeholders unanimously find this type of instrument more patient-centered than the standard pain numerical rating scale and believe that the Oswestry represents functional activities that can become impaired when they experience back issues and are important to them to overcome. Each area is scored from 0 - 5 with zero representing no limitation and five representing maximal limitation. The ten areas, which include an assessment of pain intensity, are added together, resulting in a maximum score of 50. This score is doubled and interpreted as a percentage of patient-perceived disability, with higher scores representing greater disability.

- 3.3.3 **A secondary outcome (SA3-5) is LBP-related medical resource utilization**, including 1) referrals to specialists (e.g., orthopedists, spine surgeons, physiatrists) and other health care providers, 2) tests (e.g., MRIs), surgical procedures (e.g., epidural steroid injections, laminectomy), and 3) prescription analgesics including opioids.

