### 4.3 Study enrollment procedures

4.3.1 **Subjects will be enrolled** at all of the PCP clinics selected for the trial. In keeping with the pragmatic nature of the trial, all patients will be admitted into the trial who present with a complaint of acute back pain. Recruitment (PRECIS-2 domain) is highly pragmatic being solely based on patients presenting to the clinic with back pain.

4.3.2 **Randomization:** The study is a cluster RCT; randomization of treatment arm assignment is at the clinic level, not the individual patient. Enrollment will be the same for both arms of the study.

4.3.3 **Screening procedures:** Using patient portals, clinic-based tablets, or manual questionnaires, administrative staff or clinicians at the PCP sites will administer a baseline assessment with three components that will be included in the patients’ EMR. At all sites, the EMR will be modified to accept these data elements:

- 1) The 2-item Chronic LBP Questionnaire (Appendix 1),
- 2) The 9-item STarT Back Tool to stratify risk for transition to chronic LBP and identify high risk patients (Appendix 2),
- 3) The 10-item Oswestry LBP Questionnaire (Appendix 3).

4.3.4 **Ineligibility and non-participation:** Patients with chronic LBP will be documented as not eligible and will not be enrolled for intervention or subsequent assessments. Patients refusing to complete the baseline assessments will be documented as refusing screening and not included in the enrollment for intervention or subsequent assessments.

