- A total sample size of at least 8,760 participants is needed from these sites to meet the aims of the study,
- The study needs to be conducted within the clinical setting (i.e., a pragmatic trial), which typically allows <15 minutes per patient visit; the consent/authorization procedures would disrupt the clinical setting and potentially impact patient care.

6.2.3 **Enrollment and baseline evaluation:** Upon determination of eligibility, patients will be enrolled in the QI initiative of the study. Baseline data will be contained in the EMR and extracted for study purposes, including screening results, demographic information, billing information, and clinical data (e.g., diagnoses, referrals to specialists). Patients identified as high risk, acute LBP patients in the intervention arm will be referred to PIPT, and this referral will also be captured in the EMR. The list of baseline variables to be extracted from the EMR is provided in Appendix 6.

6.2.4 **Randomization:** As a cluster RCT, randomization will occur at the clinic level and not the patient level; therefore, randomization is not a factor in the enrollment or baseline evaluation.

6.2.5 **Follow-up:** Follow-up to the initial screening and QI enrollment visit will occur through three mechanisms:

- 1) **Referral to PIPT:** For eligible patients referred to PIPT, follow up at PT will be evaluated through the checklist completed at the PT visit and returned to the PCP site. This checklist will indicate use of the PIPT approach and number of PT sessions.
- 2) **Six-month assessment:** Research staff will contact all enrolled patients 6 months after their initial visit at all sites and conduct the Chronic LBP Questionnaire and the Oswestry to assess the primary outcomes.
- 3) **Medical resource utilization:** Researchers will also extract data from the EMR at select sites to determine the secondary outcome of LBP-related medical resource utilization of tests, procedures, and pharmaceuticals by enrolled patients for 12 months after the initial visit.

The list of variables for medical resource utilization is provided in Appendix 6.

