- 9.2.4 **Treatment assignment procedures:** Detecting an interaction effect the same size as the overall intervention effect would require a four-fold increase in the effective sample size (more clinics and patients accounting for clustering), which is not feasible. There will be sufficient power to detect stronger intervention effects in some *a priori* defined subgroups at the participant level (smoking, depression, obesity, lower SES) if the cohort is evenly split.
- 9.2.5 **Analysis of randomization:** Distributions of baseline characteristics for clinics and patients will be compared between the study arms to assess effectiveness of the randomization, and statistical or clinical differences will be adjusted for in sensitivity analyses. All analyses for treatment group comparisons will use an intention-to-treat approach and results will be reported using the CONSORT extension to cluster randomized trials. This approach is highly pragmatic per the PRECIS-2 primary analysis domain.

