## 9.5 Data analyses

- 9.5.1 **Primary outcome 1:** This initial analysis (**PA1**) will use a generalized linear mixed model with a logit link controlling for block set (see Randomization) and a fixed effect for intervention accounting for the cluster RCT design with a random clinic effect. Primary analyses will also adjust for patient characteristics (maladaptive pain coping behaviors such as catastrophizing and fear avoidance, functional impairment as measured by the Oswestry, and presence

of psychiatric comorbidities), as these have been associated with higher transition to chronic LBP. The intraclass correlation coefficients will also be estimated and reported for all outcome measures to assess the assumptions for sample size analyses and also for future investigations using similar designs and outcomes. Analysis for the secondary aims (**SA4** and **SA5**) will be largely descriptive assessing the proportion of patients who transition to chronic LBP among the low and moderate risk observational cohort. The proportion and confidence interval will be estimated using generalized linear models adjusting for clustering.

- 9.5.2 **Primary outcome 2:** This aim (**PA1**) will be analyzed using contrasts from a linear mixed models analysis for 6-month back-related function (Oswestry) controlling for baseline Oswestry and the block set (see Randomization). The intervention will first be explored by time interaction, and then proceed to a main effects model with only group and time. For the secondary aims (**SA4** and **SA5**) patient-centered outcomes, such as functional status, would use general linear models if deemed appropriate based on normality assumptions. If normality is hugely violated, a cutpoint for 'response' will be applied.

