### Definition and questionnaire rules:

- “Chronic” = greater than 3 months (Q1c) + at least half the days (Q2b)
- “Acute” = all else Q1a, Q1b, or Q1c+Q2a
- If patient answers 1a or 1b, stop and patient is acute
- If patient answers 1c, proceed to question 2
- If patient answers 2a, patient is acute
- If patient answers 2b, patient is chronic

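### Free improvement: the primary PA1 model could also adjust for baseline pain duration, an already collected item of its own outcome definition, for a small gain in precision

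*Combined protocol and SAP*

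**What the plan says.** - **PA1 model (9.5.1).** A logit mixed model with intervention, block set and a random clinic effect. "Primary analyses will also adjust for patient characteristics (maladaptive pain coping behaviors such as catastrophizing and fear avoidance, functional impairment" on the Oswestry, and psychiatric comorbidities, chosen because they have been associated with higher transition. Duration is not named. The words that make the list open-ended apply only to the coping behaviors.
- **PA2 model (9.5.2).** "controlling for baseline Oswestry and the block set".
- **PA1 outcome (3.3.1).** "Chronic LBP is defined as a response of 'more than three months' to question 1", together with interference on at least half the days in question 2.
- **Entry (Appendix 1 rules).** A patient is acute, and so eligible, for "all else Q1a, Q1b, or Q1c+Q2a". On order of asking: "If patient answers 1a or 1b, stop and patient is acute". Anyone answering 2b is chronic, and 4.3.4 makes chronic patients ineligible.
- **Imbalance (9.2.5).** Baseline characteristics are compared between arms, and "statistical or clinical differences will be adjusted for in sensitivity analyses".
- **Availability.** Section 4.3.4: "Patients refusing to complete the baseline assessments will be documented as refusing screening and not included in the enrollment". Section 6.2.3: "Baseline data will be contained in the EMR and extracted for study purposes, including screening results".

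**The concern.** Question 1 has three levels at entry: less than 1 month, 1 to 3 months, more than 3 months. A patient who enters on 1c with 2a already satisfies one of the two conditions for chronic LBP; a 1a or 1b patient satisfies neither. Recorded question 2 cannot take its place if the skip rule is followed: 1a and 1b patients never reach it, and every eligible 1c patient answered 2a.

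The randomization in 3.2 balances back-pain volume and Medicaid/self-pay share across clinics, not patient duration. If duration predicts outcome, leaving it out costs some precision. It also leaves the primary estimate exposed to a chance difference between arms in the share already beyond 3 months. Under 9.2.5 the estimate adjusted for such a difference would have only sensitivity status.

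**Working it through.** **1. The plan's own power.** Inputs from 9.2.2 and 9.2.3: 30 clinics per arm, 10 to 14 completers per clinic (m), ICC 0.05, control rate 25% to 30%, 40% relative reduction. Two-sided 5% is assumed for PA1, since it is stated only for Table 3. Effective n per arm = 30m / [1 + (m − 1) × 0.05].
- m = 14, 25% vs 15%: 420 / 1.65 = 254.5, power 80.7%.
- m = 10, 30% vs 18%: 300 / 1.45 = 206.9, power 81.8%.

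Both agree with the stated value of just over 80%. That calculation uses no covariates, so the omission does not alter it.

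**2. Gain from adding question 1.** The documents give neither the duration mix nor its association with outcome, so this step rests on assumptions. A simulated random-intercept logistic model had 60 clinics, 15 block sets of 4 clinics, ICC 0.05 and duration shares 35/35/30%. Oswestry, coping and psychiatric comorbidity were in both models, each with an assumed odds ratio of 1.5 and a correlation with duration of 0.3 (0 in one variant). The information ratio is (mean likelihood ratio statistic with question 1 − 1) / (mean without − 1). It is converted to power from an 80% base by Φ(2.802 × √ratio − 1.96).

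| Assumed odds ratios (<1, 1–3, >3 months) | Information ratio | Power from 80% |
|---|---|---|
| 1/1.5/2 | 1.009 to 1.012 | 80.4% to 80.5% |
| 1/2/4 | 1.030 to 1.037 | 81.2% to 81.4% |
| 1/3/8 | 1.068 to 1.092 | 82.5% to 83.3% |

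Direct counts of rejections at 25% vs 15% (changes in percentage points, SE in parentheses):
- 12 completers per clinic: 0.0 (0.3), +1.9 (0.4) and +3.4 (0.6) for the three sets.
- Mean 18.6 completers (31 × 0.6) with CV 0.65: +1.2 (0.5) and +2.1 (0.5) for the last two sets.
- No duration effect: −0.1 (0.2).
- Type I error at 12 per clinic: 4.4% without question 1, 4.3% with it.

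A separate simulation with a cluster-level test at 12 per clinic gave −0.1, +0.9 and +2.4, with ratios 1.005, 1.030 and 1.079. The +1.9 count at 1/2/4 is the highest result for that set. The information ratio in the same setting is 1.036, which converts to +1.4, and the other counts there are +0.9 and +1.2. A fair summary is 0 to 1.5 points up to 1/2/4, and 2 to 3.5 points at 1/3/8.

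**3. Size of chance imbalance.** Completers per arm: 30 × 18.6 = 558. Design effect: 1 + [(1 + 0.65²) × 18.6 − 1] × 0.05 = 2.27, so effective n = 558 / 2.27 = 245. Assume 30% are beyond 3 months, giving variance 0.3 × 0.7 = 0.21.
- 95% range of the arm difference in that share: 1.96 × √(2 × 0.21 / 558) = ±5.4 points with no clustering of duration, and 1.96 × √(2 × 0.21 / 245) = ±8.1 points with duration ICC 0.05.
- At assumed chronic rates of 15/25/40%, patients beyond 3 months differ from the rest by 40% − 20% = 20 points. The shift in the arm difference is 0.20 × 5.4 = 1.1 to 0.20 × 8.1 = 1.6 points, either way.
- Ordinary sampling range of the arm difference: 1.96 × √[(0.1875 + 0.1275) / 245] = ±7.0 points.

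Imbalance in duration is thus a small part of the sampling error already allowed for.

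**The case against.** The strongest reply is that this is an extra covariate, not a defect. The plan selects covariates by published association with transition, and no passage says duration predicts transition in high-risk acute patients. The direction is not assured either. A 1a patient whose interference persists will also be beyond 3 months by month 6, and an eligible 1c patient has reported interference on fewer than half the days. Baseline Oswestry may already carry part of the information. All of this stands. It limits the benefit and explains why nil is inside the range, but it shows no harm from adding the item.

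Three stronger readings are tempting and are not supported:
- **That the primary result is biased or the trial underpowered by the omission.** Under randomization there is no expected bias, and the stated power never relied on covariates.
- **That adjustment rescues power when duration is imbalanced.** Looking only at trials in which imbalance happens to count against GBC+PIPT makes the gain seem large. Where imbalance happens to favor GBC+PIPT, adjustment lowers power in the same way. It corrects both directions and is not a one-sided gain.
- **That question 1 is certainly the only outcome item that varies at entry, or is a full counterpart of baseline Oswestry in PA2.** The Appendix 1 form prints both questions, the stop rule sits in a separate list, and 10.1.1 allows paper forms. Some 1a and 1b patients may therefore have answered question 2. The composite PA1 status is the same for every enrolled patient at baseline, so question 1 is one component of it and not a baseline value of the outcome.

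Section 9.2.5 does address imbalance, but it cannot alter the primary estimate.

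**Conclusion.** The point holds as an optional, free improvement (COULD). PA1 omits a baseline item that forms half of its outcome definition and decides eligibility. The expected benefit is small: about 0 to 1.5 points of power at assumed odds ratios up to 1/2/4, about 2 to 3.5 at an extreme 1/3/8, and nil if duration has no effect. The second benefit is that a chance imbalance, worth about 1.1 to 1.6 points of the arm difference at its 95% limits under the assumed rates, would be handled in the primary analysis by prior specification. Confidence is medium, because the duration odds ratios, shares, correlations, clustering and block structure are all assumed.

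**What to change.** In 9.5.1, before unblinding, add baseline Chronic LBP Questionnaire question 1 (less than 1 month, 1 to 3 months, more than 3 months) as a prespecified covariate in the primary PA1 model. Keep block set, the random clinic effect and the listed covariates.

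The cost is one sentence and two model degrees of freedom. No new collection is needed. Question 1 decides eligibility and patients who refuse the baseline assessments are not enrolled, so no patient should drop out of the model. The one thing to confirm is the extract: Appendix 6 does not list the questionnaire items, and the screening results mentioned in 6.2.3 might hold only the acute/chronic classification. Check that the item response itself is extracted at all five sites.

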### 3 Study design

#### 3.1 Primary, secondary and additional study designs

**Figure 1. Diagram of sample size by cohort and study arm**

- 3.1.1 **Primary study (PA1-2, SA3, SA5):** The primary study is a multi-site cluster RCT comparing GBC with GBC+PIPT for patients with acute LBP deemed to be high risk for transition to chronic LBP (RCT cohort). Data collection will be conducted at baseline, 6 months, and 12 months. Resource use, determined with EMR data, will be evaluated in a subset of patients.
- 3.1.2 **Secondary study (SA4-5):** A secondary ancillary prospective, observational cohort study will be conducted for those patients presenting with acute LBP

deemed to be low or medium risk. Patients with acute LBP who do not meet criteria for high risk will be identified for the prospective observational cohort. These patients will receive GBC and not be targeted with any specific study interventions, such as PIPT. Data collection will also occur at baseline, 6 months, and 12 months. The objective of this ancillary observational study is to precisely determine the rates of transition from acute to chronic LBP and resource use in the treatment of LBP.

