- 9.1.13 **H5:** GBC+PIPT will have less transition to chronic LBP and will be more effective than GBC alone for improving functional outcomes and reducing LBP-related medical resource utilization for the subgroup of patients who are underserved or with depression. Because the interventions being studied do not specifically target obesity and smoking, and the relationship of these variables to transition to chronic are unclear, group x obesity interactions are not expected.
- 9.1.14 Outcomes for this aim will utilize the same measures and sources as PA1-2, SA3 but will also include EMR data on patient co-morbidities, smoking status, and socioeconomic status.
- 9.1.15 **Missing data:** Baseline characteristics, such as age, gender, and health insurance status, will be compared between patients with complete assessment data to those with missing data by treatment group in order to assess potential biases that may exist in the complete case analysis. Sensitivity analyses for the primary and secondary outcomes will be conducted using several methods, which have different missing data assumptions.
- 1) Complete case analyses, which assumes missing data are completely at random,
  - 2) Multiple imputation using M=10 imputations, which assumes missing at random, and
  - 3) Assigning poor scores and good scores for missing values differentially by treatment group, which aligns with non-ignorable missingness (the data missingness is nonrandom and related to the actual value).

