### 9.3 Randomization, sample size and power – observational cohort

- 9.3.1 **Randomization** is not applicable to the observational cohort because moderate and low risk patients will not receive the PIPT intervention.
- 9.3.2 **Sample size** is again based on a total of 60 PCP clinics. An average of n=115 patients will be enrolled per clinic, for a total sample of N=6,900 low or medium risk acute LBP patients.
- 9.3.3 **Power:** The sample size will allow precise determination of 1) the transition rates for low risk and medium risk acute LBP who receive GBC; 2) differences between low/medium risk patients receiving GBC in the observational cohort and high risk patients receiving GBC in the intervention group; and most importantly, 3) differences among low/medium risk patients due to specific subgroup characteristics, in particular patients who are underserved, obese, depressed, or smokers. Of the three objectives, the subgroup analyses require the greatest sample size, and therefore will be described in detail here.

For the purposes of the calculations, from the literature it is assumed that low and medium risk subjects with acute LBP have an expected 20% transition to chronic. Data on obesity and smoking rates are based on national surveys. Depression rates are based on prevalence rates reported in primary care. Proportions of underserved patients are estimated from patient registries at each of the five regional sites. For the underserved, obesity, and smoking subgroups, the given sample sizes in Table 3 would be ample enough to detect at least a 30% relative difference (6% absolute difference) from 20% with powers ranging from 79% to 87%. The study would have 65% power to detect a 40% relative or 8% absolute difference (hypothesized increased rate of transition) for the depression subgroup.

**Table 3: Power** at a significance level of 0.05 to detect the specified % absolute and relative differences from a 20% chronic transition rate based on a two-sided Z-test adjusted for clustering within clinic (ICC=0.01) among 60 clinics, N=6900 enrolled and conservatively 60% response rate at 6 months in the low or medium risk population (adjusting for design effect and nonresponse N=2464).

| Subgroups (N)               | 25% relative difference
(5% absolute difference) | 30% relative difference
(6% absolute difference) | 35% relative difference
(7% absolute difference) | 40% relative difference
(8% absolute difference) |

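### The main estimate of the low/medium-risk transition rate (SA4) has no non-response adjustment, although the plan allows for 40% non-response at 6 months

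*Combined protocol and SAP*

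**What the plan says.** Section 3.1.2 gives the cohort's purpose: "The objective of this ancillary observational study is to precisely determine the rates of transition from acute to chronic LBP". Sections 9.3.2 and 9.3.3 size it: "An average of n=115 patients will be enrolled per clinic", "for a total sample of N=6,900 low or medium risk acute LBP patients". The Table 3 caption assumes "N=6900 enrolled and conservatively 60% response rate at 6 months in the low or medium risk population".

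The estimator for the SA4 rate is in section 9.5.1: "The proportion and confidence interval will be estimated using generalized linear models adjusting for clustering". No covariates, weights or imputation are named there. Section 9.5.2 plans general linear models for the SA4 Oswestry outcome and likewise names no non-response adjustment.

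Missing data are covered in section 9.1.15. It compares the baseline characteristics of patients with and without complete data, to look for bias in the complete-case analysis. It then states: "Sensitivity analyses for the primary and secondary outcomes will be conducted using several methods". The three methods are:

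- "Complete case analyses, which assumes missing data are completely at random";
- multiple imputation with 10 imputations, under missing at random;
- poor or good values assigned to missing outcomes in a way that differs between treatment groups.

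Section 9.1.15 does not say which method gives the main SA4 estimate, and it does not mention SA4 by name.

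**The concern.** SA4 asks for one marginal rate in a defined cohort. If the 60% who answer differ in outcome from the 40% who do not, the responders' rate is off by a fixed amount that a larger sample does not reduce. A narrow interval makes this worse: it looks exact but can sit beside the cohort rate.

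The PA1 comparison has two partial protections that SA4 lacks. It contrasts randomized arms, so similar response bias in both can partly cancel, and its model adjusts for several baseline risk factors. A single proportion adjusted for clustering has neither.

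At stake is the accuracy of the rate the cohort was set up to supply. The comparison in section 9.3.3 with high-risk patients receiving guideline-based care would also be affected if response patterns differ between the two groups.

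**Working it through.** **Inputs from the plan (section 9.3 and Table 3).** 6,900 enrolled, 60 clinics, 115 per clinic, 60% response, ICC 0.01, expected transition rate 20%. Table 3 counts: underserved 665 of 2,464 and depressed 184 of 2,464.

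**1. Reproduce the plan's effective sample size.**
- Completers: 6,900 × 0.60 = 4,140, or 69 per clinic.
- Design effect: 1 + (69 − 1) × 0.01 = 1.68.
- Effective N: 4,140 / 1.68 = 2,464, as stated.

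All 16 Table 3 powers also reproduce within 1 point, using a two-sided Z-test with unpooled standard error. Neither figure is in error.

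**2. Width of the SA4 interval.**
- SE = √(0.20 × 0.80 / 2,464) = 0.81 points.
- 95% half-width = 1.96 × 0.81 ≈ 1.58 points, so 18.4% to 21.6%.

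**3. Bias of the responders' rate.** The cohort rate is 0.6 × (responder rate) + 0.4 × (non-responder rate). The bias is therefore 0.4 × (responder rate − non-responder rate). For bias of absolute size b, coverage of the nominal 95% interval is Φ(1.96 − b/SE) − Φ(−1.96 − b/SE).

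With responders at 20% and assumed non-responder rates:

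| Non-responder rate | Cohort rate | Bias (points) | Coverage |
|---|---|---|---|
| 20% | 20.0% | 0 | 95% |
| 22% | 20.8% | −0.8 | 83% |
| 24% | 21.6% | −1.6 | 49% |
| 16% | 18.4% | +1.6 | 49% |

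The gap at which the bias equals the half-width is 1.58 / 0.4 = 3.95 points.

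**4. How far that threshold moves.**
- ICC 0.01 with a cluster-size coefficient of variation of 0.65 (the value section 9.2.2 uses for the randomized cohort): half-width 1.71, threshold 4.3 points.
- ICC 0.05 with equal clusters: half-width 2.56, threshold 6.4 points.
- 80% response with ICC 0.01: threshold 7.3 points.

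**5. A milder scenario tied to baseline factors.** Assume that only underserved and depressed patients have higher risk (+6 and +8 points, additive and independent) and that each factor multiplies the response probability by r. For a factor with share q and risk difference d, the share among responders is qr / (1 − q + qr). The contribution to bias is d × (that share − q).

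With q = 665/2,464 = 0.270 and 184/2,464 = 0.075:

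| r | Underserved | Depressed | Total bias (points) | Coverage |
|---|---|---|---|---|
| 0.9 | −0.12 | −0.06 | −0.18 | 94% |
| 0.8 | −0.25 | −0.11 | −0.36 | 93% |
| 0.7 | −0.39 | −0.17 | −0.56 | 89% |

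The risk differences and response ratios are assumptions; the documents report no response by subgroup.

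**The case against.** The strongest reply is that section 9.1.15 already covers this. It checks responders against non-responders and plans imputation for secondary outcomes, so both estimates would be produced, and the request only changes which is main and which is sensitivity. Section 9.5.1 also calls the SA4 analysis largely descriptive, and no decision rule hangs on it. Much of this stands: the risk is not ignored. What remains is that the plan never says which estimate leads, gives no rule if the baseline comparison shows imbalance, and has no non-ignorable scenario that fits a single cohort.

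It is also fair to say that a responder-only main estimate is an inference. Section 9.5.1 does not say that the analysis is unweighted or restricted to responders, and section 9.1.15 lists complete case among the sensitivity methods. It remains the likeliest reading, because 9.1.15 also treats the complete-case analysis as the one whose bias is to be checked.

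A reader might take Table 3 to mean that the plan expects transition to differ by 5 to 8 points in all four subgroups. With +6 points for underserved, obese and smoking patients, +8 for depressed patients, and lower response in all four, the bias would be about −0.4 to −1.2 points for r from 0.9 to 0.7. The documents do not support that reading. Table 3 lists detectable differences, and sections 1.2.5 and 9.1.13 describe the role of obesity and smoking as uncertain or unclear.

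Nor does it follow that the subgroup differences, which section 9.3.3 ranks as the most important objective, are biased. With independent factors and additive risks, the differences among responders are unchanged.

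**Conclusion.** The point holds as a recommended change to a secondary analysis. The SA4 rate is planned with an interval of about ±1.6 points that carries no allowance for 40% non-response, and the plan's only adjustment for it is a sensitivity analysis.

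The harm is conditional. There is no bias if non-responders transition at the responders' rate, and the plan itself calls 60% response conservative. An assumed gap of 2 points lowers coverage to about 83%, and one of 4 points to about 49%. If the gap arises only through underserved and depressed status, as assumed in step 5, the loss is small: 0.2 to 0.6 points, with coverage of 94% to 89%.

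A reader might infer that adjustment would restore the 49% case to 95%. It would remove only the part of the gap explained by baseline variables, and the documents do not say how large that part is.

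**What to change.** In section 9.5.1, and for the SA4 Oswestry outcome in 9.5.2:

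- State that the main SA4 estimate refers to all enrolled low- and medium-risk patients.
- Obtain it by the multiple imputation already planned or by inverse-probability-of-response weighting. Base either on baseline variables held for enrolled patients: STarT score, Oswestry, question 1 of the Chronic LBP Questionnaire, demographics, insurance, BMI, tobacco use, comorbidities and clinic. Use a clinic-clustered variance.
- Report the responder-only result as the sensitivity analysis.
- For SA4, replace the scenario defined by treatment group with a cohort-level range in which the non-responders' rate is shifted by stated amounts. At 60% response, each 1-point shift moves the cohort rate by 0.4 points.

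The cost is a few lines of text and some extra analysis, with no added patients or follow-up. The interval may be slightly wider, and bias from unmeasured reasons for non-response remains. Use of non-responders' baseline records depends on each site's IRB terms: sections 6.2.2 and 11.1 record the medical-record waiver for UPMC and Intermountain and leave the other three sites to separate review. This should be confirmed before the method is fixed.
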